Statistical Considerations:	
The effectiveness of cooling on recovery and performance are tested on:
 
Repeated measures analysis of variance (MANOVA) factors:
 
Protocol A
 
- Task (Cooling vs. Thermoneutral application)- Time (These factors are measured immediately after cooling and 24 hours, 48 hours and 72 hours after the interventions) 
Protocol B
 
Task (cooling vs. thermoneutral application)
 
Time (These factors are measured immediately after cooling and 24 hours, 48 hours and 72 hours after the interventions)
 
The significance level is $P < 0.05$, the statistical data analysis is carried out with SPSS 22.

GCP Statement:	This study will be conducted in compliance with the protocol presented here, the current version of the Declaration of Helsinki, the ICH-GCP, ISO EN 14155 (as far as authoritative), and the Swiss Human Research Ordinance HFV.

SUPSI

Overview of the study

Cold therapy, such as cold water immersions and ice packs, has long been known as post-activity recovery strategies. Sports with different levels of intensity lead to different levels of exhaustion of the body's musculoskeletal, neuronal and metabolic systems. Exercise can also lead to microscopic injuries in muscle tissue, colloquially known as muscle soreness. In sports physiotherapy and rehabilitation, cold therapy has long been used as a post-activity intervention to alleviate these subjective symptoms. This is also confirmed by the current scientific knowledge base (Ascenso et al. 2011, Banfi et al. 2010, Crystal et al. 2013, Delextrat et al. 2013, u.a.). Cold therapy is usually referred to as a procedure which aims to alleviate pain symptoms and inflammatory processes.

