5.1 Primary outcomes

Muscle activity (EMG)

Increased activation of a muscle can be measured in a larger amplitude of the EMG signal. For this purpose, the absolute amplitude [mV] and the Integral over a certain time interval [mVs] are used in this study.

MVIC is measured on the Cor 1 - ergometer chair [Nm] in 90° knee flexion. The measurement moments take place directly, 24 hours, 48 hours and 72 hours after the intervention.

Jump height measurement

The jump height after the load is determined with a jump height measuring plate designed for this purpose (Just Jump Plate, Probotics Inc., Huntsville, USA). The test subjects assume a standing position on the plate. The test subjects are allowed to start from the squatting position (countermovement jump) to measure the jump height. The arms must be placed at the hips during the entire movement. The measurement moments take place directly, 24 hours, 48 hours and 72 hours after the intervention.

Subjective muscle soreness

The subjects reported their subjective feeling of muscle soreness on a visual analogue scale (VAS). The scale will be scaled from "0" (no muscle soreness present) to "10" (largest imaginable muscle soreness) in cm increments. The measurement moments take place directly, 24 hours, 48 hours and 72 hours after the intervention.

Subjective information on general exhaustion

The subjects indicate their subjective general feeling of exhaustion on a visual analogue scale (VAS). The scale is from "0" (no general exhaustion present) to "10" (greatest conceivable general exhaustion) can be scaled in cm steps. The measurement moments take place directly, 24 hours, 48 hours and 72 hours after the intervention.

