9.1 Schedules of the various protocols

1. *Subject Information & Informed Consent*

10 Min

2. *Preparation of the subject*

15 min

3. *Running the Test Log (Sublogs)*

Partial Protocol A: first measurement + intervention - approx. 60 min	
Cooling vs. Thermoneutral application on recovery	
Cooling panel	Thermoneutral Application Group
1. 3 x Vertical Leaps VAS & BARROW (max 5 min)	1. 3 x Vertical Jumps, VAS & BARROW (max 5 min)
Max 1 min break	Max 1 min break
2. 1 minute max vertical Leaps, VAS & BARROW (1 min)	2. 1 minute max vertical jumps, VAS & BARROW (1 min)
Max 5 min break	Max 5 min break
3. Cooling (20 min)	3. Thermoneutral application (20 min)
Max 1 min break	Max 1 min break
4. 3 x Vertical Leaps, VAS & BARROW (max 5 min)	4. 3 x Vertical Jumps VAS & BARROW (max 5 min)
Directly after the Intervention	immediately after the intervention
5. 3 x Vertical Leaps, VAS & BARROW (max 5 min)	5. 3 x Vertical Jumps, VAS & BARROW (max 5 min)
24 hours after the intervention	24 hours after the intervention
6. 3 x Vertical Jumps, VAS & BARROW (max 5 min)	6. 3 x Vertical Jumps, VAS & BARROW (max 5 min)
48 hours after the intervention	48 hours after the intervention
7. 3 x Vertical Leaps, VAS & BARROW (max 5 min)	7. 3 x Vertical jumps, VAS & BARROW (max 5 min)
72 hours after the intervention	72 hours after the intervention

SUPSI

Partial Protocol B: first measurement + intervention - approx. 60 min	
Cooling vs. Thermoneutral application on performance	
Cooling panel	Thermoneutral Application Group
1. 1 x MVIC, VAS & BORG (max 3 min) Max 1 min break	1. 1 x MVIC, VAS & BORG (max 3 min) Max 1 min break
2. Cooling (20 min) Max 1 min break	2. Thermoneutral application (20 min) Max 1 min break
3. 60 % MVIC for 1 min (2 min) Max 5 min break	3. 60 % MVIC for 1 min (2 min) Max 5 min break
4. 1 x MVIC, VAS & BORG (max 5 min) immediately after the intervention	4. 1 x MVIC, VAS & BORG (max 5 min) immediately after the intervention
5. 1 x MVIC, VAS & BORG (max 5 min) 24 hours after the intervention	5. 1 x MVIC, VAS & BORG (max 5 min) 24 hours after the intervention
6. 1 x MVIC, VAS & BORG (max 5 min) 48 hours after the intervention	6. 1 x MVIC, VAS & BORG (max 5 min) 48 hours after the intervention
7. 1 x MVIC, VAS & BORG (max 5 min) 72 hours after the intervention	7. 1 x MVIC, VAS & BORG (max 5 min) 72 hours after the intervention

Sub-protocol	Total time commitment	Visits
A	Approx. 80 min	Once 60 min and 3 times for max 5 min

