11 STATISTICAL METHODS

11.1 Hypotheses & Factors

Subprojects A and B

Subproject A

Jump height (cm)

HO The jump height is not increased by the post-activity cooling compared to thermoneuapplication during a 72-hour recovery period.

H1 The Jump height becomes through the Post-activity cooling increased opposite thermoneutral application during a 72-hour recovery period.

Subjective muscle soreness (VAS)

HO The subjective muscle soreness information is not reduced by post-activity cooling compared to thermoneutral application for 72 hours.

H1 The subjective muscle soreness information is lower due to post-activity cooling compared to thermoneutral application for 72 hours.

Subjective data on general exhaustion (BORG)

HO The subjective information on general fatigue is not reduced by post-activity cooling compared to thermoneutral application for 72 hours.

H1 The subjective data on general fatigue are lower with post-activity cooling compared to thermoneutral application for 72 hours.

Subproject B

MVIC (mV)

HO MVIC performance is measured by the pre-activity cownot increased compared to thermoneutral application for 72 hours

H1 The MVIC Efficiency is increased by pre-activity cooling compared to thermoneutral application for 72 hours

Subjective muscle soreness (VAS)

HO The subjective muscle soreness data is not reduced by the pre-activity cooling compared to thermoneutral application for 72 hours.

H1 The subjective muscle soreness is lower due to the pre-activity cooling compared to thermoneutral application for 72 hours.

SUPSI

Subjective data on general exhaustion (BORG)

H0 The subjective information on general fatigue is not reduced by pre-activity cooling compared to thermoneutral application for 72 hours.

H1 The subjective information on general fatigue is lower due to pre-activity cooling compared to thermoneutral application for 72 hours.

A 2-factor analysis will be carried out in both projects. Factor 1:

Intervention (cooling vs. Thermoneutral application) Factor 2:

Time (0, 24 hours, 48 hours, 72 hours)

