11.4.2 Primary Analysis

The statistical data analysis is carried out by [name]. [name] after completion of the data collection of the respective sub-protocol.

Repeated measures analysis of variance (MANOVA)

2 factors:

Protocol A

Intervention (cooling vs. Thermoneutral application) Time

(0, 24 hours, 48 hours, 72 hours)

SUPSI

Protocol B

Intervention (cooling vs. Thermoneutral application) Time

(0, 24 hours, 48 hours, 72 hours)

The significance level is set at $P < 0.05$, and the statistical data analysis is carried out with SPSS 22.

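### Subproject A collects VAS and BORG ratings after the load and before the application but gives them no role in the analysis, which costs precision in a very small comparison

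*Combined protocol and SAP*

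**What the plan says.** The schedule for subproject A in section 9.1 has two ratings before the application. Step 1 is at rest, with the baseline jumps: "1. 3 x Vertical Leaps VAS & BARROW (max 5 min". Step 2 follows the exhausting load: "2. 1 minute max vertical Leaps, VAS & BARROW (1 min". I read the garbled scale name as BORG. A break of up to 5 minutes comes next, then cooling or the thermoneutral application as step 3. Steps 4 to 7 are the ratings directly afterwards and at 24, 48 and 72 h.

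The primary analysis in section 11.4.2 is "Repeated measures analysis of variance (MANOVA" with two factors, intervention and time. The time levels are "0, 24 hours, 48 hours, 72 hours", as in section 11.1. The synopsis, under statistical considerations, fixes the first level: "Time (These factors are measured immediately after cooling and 24 hours, 48 hours and 72 hours after the interventions". Section 5.1 gives the same four occasions for both ratings: "The measurement moments take place directly, 24 hours, 48 hours and 72 hours after the intervention". No covariate or change score is named, and section 11.4.3 says there is no secondary analysis. Section 3.1 mentions ratings before and after the load and links a baseline to the three jumps, but gives neither a place in the model.

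The soreness hypothesis for subproject A in section 11.1 is a between-arm statement: "The subjective muscle soreness information is lower due to post-activity cooling compared to thermoneutral application for 72 hours". The exhaustion hypothesis has the same form.

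**The concern.** Two of the three primary outcomes in subproject A are these ratings, and section 4.2 calls them recovery parameters. How sore or exhausted someone is after the load may well carry over into later ratings. Section 8.1.1 lets participants stop the load at their personal limit, so post-load states can differ between people. Step 2 comes before the application, so the application cannot have changed it, and it is a legitimate covariate in subproject A. The same would not hold for a post-load rating in subproject B, where the load follows the application.

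Step 1 may be a weaker substitute for these two outcomes, because rested healthy volunteers probably rate near 0 (my assumption; the documents give no values).

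At stake is the precision of a comparison whose size is capped for financial reasons (synopsis, number of participants). The measurement that might improve it is already being taken.

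**Working it through.** **Inputs from the documents.** 20 participants in subproject A (11.2). Significance level 0.05 (11.4.2), taken as two-sided because sidedness is not stated. The allocation ratio is not given; an equal split means 10 per arm. Section 10.3 refers to 20 or fewer per experimental group and section 6.1 is unclear on group size, so 20 per arm is shown as well.

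**Assumed.** The correlation r between the step-2 rating and a later rating. The documents give no correlation, SD, effect size or power, so there is no figure of the plan's own to reproduce.

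**1. Chance imbalance at step 2.** The difference between arm means has standard deviation sqrt(2/n), in units of the between-person SD.
- 10 per arm: sqrt(2/10) = 0.447. The probability of a difference beyond 0.5 SD is 26%.
- 20 per arm: sqrt(2/20) = 0.316. That probability is 11%.

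**2. Carry-over into an unadjusted later comparison.** An imbalance of one standard deviation moves the later difference by r × sqrt(2/n).
- 10 per arm: 0.13, 0.22 and 0.31 SD at r = 0.3, 0.5 and 0.7.
- 20 per arm: 0.09, 0.16 and 0.22 SD.

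This movement is part of the unadjusted standard error, not an addition to it. At r = 0.5 and 10 per arm, 0.22 is half of the standard error of 0.447.

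**3. Gain from adjustment at one time point.** The expected variance ratio, adjusted to unadjusted, is (1 − r²)(N − 3)/(N − 4). With N = 20 the last factor is 17/16 = 1.0625. The interval-width ratio is the square root of the variance ratio times t(17)/t(18) = 2.1098/2.1009 = 1.0042.

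| r | Variance ratio | CI width ratio | Change |
|---|---|---|---|
| 0 | 1.0625 | 1.035 | +3.5% |
| 0.3 | 0.967 | 0.987 | −1% |
| 0.5 | 0.797 | 0.896 | −10% |
| 0.7 | 0.542 | 0.739 | −26% |

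At r = 0.5 the gain is worth about 25 participants instead of 20 (20/0.896² = 24.9).

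**4. Break-even.** Set (1 − r²) × 1.0625 × 1.0042² = 1. Then r² = 0.067 and r is about 0.26. Below that, adjustment widens the interval.

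**5. If there are 20 per arm.** With N = 40 the factor is 37/36 = 1.028 and t(37)/t(38) = 1.0009. The width changes are +1.5%, −3%, −12% and −28% at r = 0, 0.3, 0.5 and 0.7.

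**The case against.** The strongest reply is that nothing here is invalid. Sections 6.2.1 and 7.3 allocate by lot in sealed envelopes, so the p-value and interval of the unadjusted analysis already allow for chance imbalance at step 2. A reader might infer that an imbalance biases the comparison or makes a cooling effect impossible to recognise. The documents do not support that. An imbalance can push the estimate of one realised trial away from the truth, but the test keeps its error rate over repeated randomisations. This part of the reply stands in full.

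Second, the gain depends on an undocumented r. Soreness rated within a one-minute slot may be near 0 for nearly everyone, and exhaustion straight after jumping may say little about general exhaustion one to three days later. A single r for all four times is a simplification, and r may be lower at 24 to 72 h. This stands, and is why the range and the break-even are shown.

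Third, a reader might take step 2 as the exact state in which the application begins. Section 9.1 allows up to 5 minutes between them, in which exhaustion may fall by differing amounts. Step 2 is the last rating before the application, no more. It remains a valid covariate.

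Fourth, an intervention-by-time term would compare within-person change and remove stable differences in level. That is true, but its first level is the rating after the application, so it does not replace a pre-treatment covariate. The point bears mainly on the between-arm main effect.

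Fifth, "Time (0, 24 hours, 48 hours, 72 hours" could by itself be read as including a baseline at 0. The synopsis excludes that reading.

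Finally, the gap is wider than this: step-1 jump height in A and the step-1 measures in B are also absent from the model. That does not weaken the point.

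**Conclusion.** The point holds as one of precision. A pre-treatment rating of two primary outcomes in subproject A is scheduled, and no analysis uses it. The unadjusted test is valid, and no figure in the documents is shown to be wrong.

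At 10 per arm the benefit of adjustment is negligible at r = 0.3, useful at 0.5 and large at 0.7. Below about 0.26 there is a small loss. These figures rest on an equal split, a two-sided 5% level, one time point analysed by ANCOVA, and an r that the documents cannot supply. With 20 per arm the chance imbalance is smaller, and the conclusion is the same.

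**What to change.** In section 11.4.2, for VAS and BORG in subproject A, pre-specify the participant's own step-2 rating of the same scale as covariate in the between-arm comparison. Centre it at its overall mean, so that the test of time stays interpretable, and include a covariate-by-time term, since its relation to the outcome need not be the same at 0 and 72 h. Report the mean step-2 rating by arm. State in the same place that time 0 is the rating directly after the application.

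The cost is a few lines of text, handled as a protocol change under sections 2.3 and 2.10; no new measurement is needed. Statistically, the covariate uses one between-person degree of freedom and its interaction with four time levels uses three within-person ones (4 − 1). If step 2 predicts nothing, the single-time-point interval is 3.5% wider at 10 per arm.

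This should be settled before results are seen. Section 12.4 has results and statistical analyses presented in monthly reports to the study supervisor, and section 11.4.6 would treat a later addition as a deviation to be justified.

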9.2 Measuring outcomes

ICH: Specification of the efficacy parameters. Specification of safety parameters.

Sub-protocol	Total time commitment	Measurement parameters
A	Approx. 80 min (1x 60 min & 3 x 5 min)	Measurements: Jump height VAS & BORG
B	Approx. 80 min (1x 60 min & 3 x 5min)	Measurements: MVIC VAS & BORG

SUPSI

9.2.1 Measurement of primary outcomes

ICH: Methods and timing for assessing, recording, and analysing of efficacy & safety parameters.

The following data are collected during all tests described in the sub-protocols in chap. 9.1.

MVIC of the ventral thigh muscles

Muscle activity is measured using the sEMG active sensors wireless surface electromyogram system from PLUXwireless bodysignals S.A. (physioplux.com). Skin-friendly electrodes from Synmedig AG are used: Ambu® Blue Sensor N. MVIC is measured on the Cor 1 - ergometer chair [Nm] in 90° knee flexion.

The electrodes are placed according to the internationally recognized SENIAM guidelines (SENIAM project 2013).

Jump height (cm)

The jump height after the load is determined with a jump height measuring plate designed for this purpose (Just Jump Plate, Probotics Inc. , Huntsville, USA). The test subjects assume a standing position on the plate. The test subjects are allowed to start from the squatting position (countermovement jump) to measure the jump height. The arms must be placed at the hips during the entire movement (countermovement jump).

Subjective muscle soreness (VAS)

The subjects reported their subjective feeling of muscle soreness on a visual analogue scale (VAS). The scale will be scaled from "0" (no muscle soreness present) to "10" (greatest conceivable muscle soreness) in cm steps.

Subjective data on general exhaustion (BORG)

The subjects indicate their subjective general feeling of exhaustion on a visual analogue scale (VAS). The scale is from "0" (no general exhaustion present) to „10" (greatest conceivable general exhaustion) can be scaled in cm steps.

9.2.2 Measurement of secondary outcome

None available

9.2.3 Survey of further outcomes

None available

9.2.4 Collection of safety parameters

No corresponding parameters are collected.

SUPSI

9.2.4.1

9.2.4.2 Adverse events

9.2.4.3 Laboratory parameters

9.2.4.4 Vital signs

SUPSI

9.2.5 Collection of data in case of early termination of studies

For the participants, there is no disadvantage in the event of an (arbitrary) discontinuation of study participation and no further interventions are necessary for follow-up treatment.

However, if the study participation was discontinued due to an injury occurred during the study participation, this will be recorded and reported to the sponsor investigator (head of the research laboratory), study leader and supervisor of the study. The report is then sent to the business liability insurance of Thim van der Laan University College Physiotherapy in Landquart.

The following are recorded:

- Date and time of the incident
- Course of the incident
- Persons involved & witnesses Study
- ID (assigned by the CEC)
- Personal details of the person concerned (if not previously recorded)

SUPSI

9.3 Procedure at each visit of the test subjects

9.3.1 Single measurement

Sub-protocols A and B are multiple visits.

9.3.2 Multiple visits

(e.g. Visit 1, Baseline (Day e.g., 1): List all exams/tests, actions to be performed according to flow chart (9.1) including also e.g., Dispense of trial medication, Scheduling of next visit)

The sub-protocols A and B are multiple visits with a duration of about 80 minutes each, which takes place as follows:

1. Subject Information & Informed Consent

The subjects will be comprehensively informed about the process and possible risks before they are confirmed to participate in the study. You will also receive the information in written form and have the opportunity to ask questions. The declaration of consent explains to them what their rights and obligations are when participating and that they may withdraw from participation at any time without giving reasons, without incurring any disadvantages as a result. More detailed information can be found in Chapter 2.7.

2. Preparing the subject

If the subject is willing to participate, he or she is instructed to change in a separate room:

- Subproject A

this sub-project does not require any further preparations.

- Subproject B

First, the areas for the placement of the electrodes are marked with a skin-friendly pen (eyeliner) and, if necessary, individual areas of the EMG electrode placements are shaved (both were explained to the test subject beforehand according to a checklist). Then the electrodes are attached.

3. Measurements

The tests are carried out in the same way as in the corresponding sub-protocol and the data is collected.

4. Indemnification and Conclusion

After completion of the individual measurement, the test subject is asked to change again in a separate room. Afterwards, they are asked how they are feeling. The subject is asked to report back to the laboratory at intervals of 24 hours (up to a maximum of 72 hours) to carry out the follow-up measurement. After completion of the measurements, the test subject will be happy to receive the compensation to which he/she is entitled. Information in the advertisement:

Flat rate Str. 200 .- after completion of the 72-hour measurement.

SUPSI

Subproject A

In subproject A, the subjects return to the laboratory 24 hours, 48 hours and 72 hours after the intervention. Here, the maximum jump height during 3 attempts is determined again. Furthermore, the subjective muscle soreness and general states of exhaustion are recorded.

Subproject B

In subproject B, the subjects return to the laboratory 24 hours, 48 hours and 72 hours after the intervention. Here the MVIC is determined again. Furthermore, the subjective muscle soreness and general states of exhaustion are recorded.

SUPSI

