- Pacemakers & cardiac arrhythmias
- Known circulatory problems Pregnancy
- Diagnosed skeletal static deviations
- Appendectomy less than 2 years ago
- Raynaud's syndrome

The subjects will be comprehensively informed about the process and possible risks before they are confirmed to participate in the study. You will also receive the information in written form and have the opportunity to ask questions. The declaration of consent explains to them what their rights and obligations are when participating. In addition, they are informed that they may withdraw from participation at any time without giving reasons, without incurring any disadvantages as a result.

SUPSI

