5.3 Safety Aspects

No further outcomes are included that serve safety.

Stopping the experiment is up to the testers' assessment of the subject's resilience. If this is estimated to be too low, the examiner can discontinue the experiment.

If, according to his or her own subjective assessment, the subject does not feel well, he or she can discontinue the experiment and withdraw his or her participation in the study. There are no disadvantages for him as a result.

SUPSI

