7.2 Recruitment and screening

(ClinO, Art 25, Appendix 3, 1.4 & 1.6; AGEK 5.1; SPIRIT #15)

Recruitment

It is advertised on the website (homepage & Facebook) of Thim van der Iaan University College Physiotherapy. The exact texts have been prepared according to the checklist of the Cantonal Ethics Commission Zurich.

SUPSI

As an advertisement (text visible):

- Homepage of the Thim van der Laan Physio School: www.Physio school.Ch
- Facebook page of the Thim van der Laan Physiotherapy School: <https://www.facebook.com/physioschule>

Screening

At the first contact, the pot. Participant informs about the course and risks of the study, as well as the conditions for and the amount of compensation. A checklist for contacting them by telephone serves as a basis.

During the first telephone contact, a questionnaire is filled out by the study management to determine the suitability as a study participant.

Advertisements, questionnaires and checklists for the first contact can be found in the supplement.

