7.4 Discontinuation of study participation

If a participant withdraws from the study, the lot of the allocation is returned to the pot in a new envelope and a new participant is sought.

The already completed consent form is stored in the locked filing cabinet, data that has already been collected is stored, but is not included in the further data analysis of the study.

The conditions for the termination of the experiment were described in chap. 5.4.

There is no disadvantage for the participants if they discontinue their participation in the study.

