8 STUDY INTERVENTION

8.1 Medical Product ID

8.1.1 Intervention Product

Zamar Therapy

Zamar Therapy is a certified medical device according to European directives (Directive 93/42/EEC and ISO 13485:2012). The temperature can be reduced from -5.0°C to $+45^{\circ}\text{C}$. The maximum adjustable treatment time is 1 hour. Cuffs ensure optimal contact with the corresponding body region. A coolant circulates continuously between the device and the man's boot.

This device is used for the following indications: treatment of the musculoskeletal system (contusions, contractures, lesions of the second degree, hematomas), tendinogenic system (tendinitis, tenosynovitis, tendinopathy), bone-cartilage system (contusions, post fractures), capsuloligamentary system (sprains, torsions, Contusions of ligaments), postoperative, aesthetic surgery and to accelerate recovery time.

In this study, temperatures of $+8^{\circ}\text{C}$ and thermoneutral temperatures ($+32^{\circ}\text{C}$) are used for 20 minutes.

Fig. 1: Zamar Therapy (www.zamarmedical.com)

Securing the test subjects

The temperature of 8°C is a cooling temperature commonly used in the literature (cf. Ascensao et al., 2011; Bailey et al., 2007; Crystal et al., 2013; Delextrat et al., 2013; Ingram et al., 2009; Jakeman et al., 2009; King et al., 2009; Leal et al., 2011; Paddon-Jones et al., 1997; Pointon et al., 2011; Pointen et al., 2012; Sellwood et al., 2007; Yanagisawa et al., 2003). Nevertheless, the test subjects can stop the cold treatment at any time if they feel unwell.

During the maximum and submaximal loads, the test subjects go to their personal performance limit. Although they are motivated by the examiners, they are not encouraged to exceed the personal performance threshold. The test subjects can be used in case of discomfort or if the personal performance limit is reached, stop the loads at any time. Furthermore, 2 examiners will be next to the subject during the jumping load in order to be able to catch him/her in case of circulatory problems. An emergency kit is available at all times during the examinations (see Chapter 3.7. Risk/ Benefits).

SUPSI

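### The only payment rule shown is one flat sum tied to the 72-hour measurement, which does not fit the repeated statement that leaving the study brings no disadvantage

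*Combined protocol and SAP*

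**What the plan says.** Step 4 of section 9.3.2 deals with payment. It says "After completion of the measurements, the test subject will be happy to receive the compensation to which he/she is entitled" and then cites the advertisement: "Flat rate Str. 200 .- after completion of the 72-hour measurement". Section 7.2 says that callers are told about the course and risks of the study, "as well as the conditions for and the amount of compensation", but does not list those conditions.

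The assurances about leaving are spread through the protocol:

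- Sections 3.8 and 9.3.2 both say that "they may withdraw from participation at any time without giving reasons, without incurring any disadvantages as a result".
- Section 5.3 lets a participant who feels unwell stop and withdraw: "There are no disadvantages for him as a result".
- Sections 7.4 and 8.5 both say "There is no disadvantage for the participants if they discontinue their participation in the study".
- Section 9.2.5 says "there is no disadvantage in the event of an (arbitrary) discontinuation of study participation".
- Section 2.7 adds that leaving has no personal consequences.

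On stopping a procedure, as distinct from leaving the study, section 8.1.1 says "Nevertheless, the test subjects can stop the cold treatment at any time if they feel unwell" and gives a similar right for the loads. Section 5.3 also lets the examiner end the experiment.

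**The concern.** A lump sum that falls due only on completion makes leaving cost money. If a participant who feels unwell gives up 200 by withdrawing, the assurance in section 5.3 is not accurate for the person it was written for. The payment then gives a reason to carry on when the protocol wants people to feel free to stop.

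This matters because the participant's own judgement carries weight here. For the cold application, the right to stop is the only safeguard that section 8.1.1 names apart from the literature basis for the temperature. During the loads, participants are taken to their personal limit and may stop. Section 9.2.4 says that no safety parameters are collected, so an incentive to stay and say nothing is unwelcome. At stake are voluntariness, the accuracy of what participants are told, and to some extent the disclosure of harm.

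**Working it through.** The check is mainly a comparison of text. The plan states no figure to reproduce.

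**Step 1: is payment conditional, or only dated?** Section 9.3.2 gives one flat sum linked to one completion event. Section 7.2 says that compensation has conditions, and the only one visible is completing the 72-hour measurement. No section gives a payment per visit or in part. No section says outright that an early leaver receives nothing. Conditional payment is the ordinary reading, but it is an inference.

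**Step 2: can that reading stand beside the assurances?** Six sections (3.8, 5.3, 7.4, 8.5, 9.2.5 and 9.3.2) promise no disadvantage, and 2.7 promises no personal consequences. Losing the whole payment is a disadvantage in the plain sense. Section 9.3.2 contains both statements, the assurance in step 1 and the payment line in step 4. The assurances concern the participant's own decision to leave. What is paid when the examiner ends participation is not covered at all.

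**Step 3: how much has been given by the end of visit 1?** Section 9.1 schedules one visit of 60 minutes and three of at most 5 minutes.

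- From the visit lengths: 60 / (60 + 3 × 5) = 60 / 75 = 80%.
- From the stated total of about 80 minutes: 60 / 80 = 75%.

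In both sub-protocols, visit 1 also contains the 20-minute application and the one-minute load. Under all-or-nothing payment, someone who leaves after it receives 0 of 200. If the line fixes only the date of payment, the loss lies somewhere between 0 and 200, and the text does not say where.

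**Step 4: what would payment on early exit cost?** The inputs are 40 participants (synopsis) and 200 each. The share who stop early is not in the documents. I assume 5% to 15%.

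- Payment to 40 completers: 40 × 200 = 8,000.
- Early stoppers: 0.05 × 40 = 2 to 0.15 × 40 = 6.
- Extra if every stopper is paid in full and replaced: 2 × 200 = 400 to 6 × 200 = 1,200.
- Extra above 8,000 if none is replaced: 0.

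Both replacement cases are needed because section 7.4 says that a new participant is sought and section 11.4.1 says that none is.

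**The case against.** The strongest reply is that forfeiture is nowhere stated. The line may only fix when payment is made. It is a short extract from an advertisement, and the full advertisement, the contact checklist and the subject information are appendix items outside the text reviewed. A part-payment rule may stand there. The consent documents also go to the ethics committee for approval (2.7), and the advertisement was prepared from that committee's checklist (7.2). This stands as a limit on certainty: the conflict is probable, not explicit. It does not remove the need for section 9.3.2 to state the rule.

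In sections 8.5 and 9.2.5 the assurance is joined to a remark about follow-up treatment, so there it need not concern money. That is fair, but 3.8, 5.3, 7.4 and 9.3.2 carry no such limit.

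A reader might infer three stronger points that the documents do not support:

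- **That stopping the cuff or cutting a load short loses the payment.** Section 8.1.1 does not say that this ends participation. Such a person could still attend at 72 hours and meet the quoted condition.
- **That the right to stop is the main protection.** The protocol does not rank its protections. Sections 3.7, 5.3 and 8.1.1 also name two examiners beside the jumper, an emergency kit, a defibrillator and the examiner's power to stop.
- **That staying in for the money keeps injuries out of the record.** Sections 8.5 and 9.2.5 do record injuries that end participation. However, 10.3 requires an injury arising from a circulatory problem to be logged and reported at once, and 9.3.2 has participants asked how they feel. Under-reporting is a residual risk, not a consequence that can be shown.

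The exhausting load also occurs only at visit 1. Later visits are three jumps or one MVIC, in at most 5 minutes, so the physical exposure that the payment encourages after visit 1 is small.

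**Conclusion.** The point holds in limited form. The flat payment is tied to the 72-hour measurement, no part payment is stated, and on the ordinary reading this is inconsistent with the no-disadvantage statements. The most that a leaver can lose is 200, after giving 75% to 80% of the scheduled time if they leave after visit 1. The least is 0, if the line only sets a date.

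The conclusion assumes that the advertisement and the subject information contain no part-payment rule. If they do, what remains is that section 9.3.2 omits it. The point applies to withdrawal and to participation ended through injury or by the examiner, not to pausing or shortening a procedure. It concerns consent and participant protection, and no sample size, error rate or analysis depends on it. The change should be made because it is cheap and removes an inconsistency in what participants are told.

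**What to change.** In section 9.3.2, the advertisement and the subject information, replace the completion-only rule with wording such as: compensation is paid in full if participation ends because of discomfort, injury or the examiner's decision, and pro rata for attended visits if the participant withdraws for any other reason.

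Define the pro rata share, because the choice matters. Equal shares over four visits give 200 / 4 = 50 after visit 1. Shares by scheduled minutes give 200 × 60 / 75 = 160. State also that shortening a cooling session or a load while remaining in the study does not affect payment, if that is the intention. Keep all the no-disadvantage statements, since deleting them to remove the inconsistency would weaken protection.

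The cost is wording in three places and submission to the ethics committee under sections 2.7 and 2.10. Extra payments are at most about 400 to 1,200 under the assumed 2 to 6 early stoppers, all replaced and all paid in full. Pro rata payment would make this less. The incentive to complete becomes slightly weaker. That has some price here, because sections 11.3 and 11.5 exclude anyone who does not finish, so each additional early leaver removes a whole record from the analysis.
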